8 TREATMENT

8.1 Intervention

This will be a 2-arm randomized, double-blind, controlled trial. The therapeutic intervention will be treatment with either sacubitril/valsartan or placebo. Study drug will be given for 12 weeks

(+/- 1 week).

8.2 Drug Dispensing

Sacubitril/valsartan and matching placebo will be provided to Duke University Hospital by Novartis Pharmaceuticals. Participants will receive a sufficient supply of study drug at each study visit to last until the next study visit by a blinded member of the study team. Drug storage, inventory, accountability, and dispensing will be managed at Duke University Hospital. Participants will be instructed to take the medication as required by the protocol and compliance will be assessed at each visit.

8.3 Drug Administration

Subjects will take sacubitril/valsartan or placebo twice daily by mouth, with dosing determined as outlined in Section 6 above.

8.4 Drug Storage Requirements

Study medication must be received by designated personnel at Duke University Hospital, handled and stored safely and properly, and kept in a secured location to which only the investigator and designated site personnel have access. Upon receipt, doses of sacubitril/valsartan and matching placebos should be stored according to the instructions specified on the drug labels.

8.5 Drug accountability

Participants are instructed to return all used, partly used and unused trial product at each study visit. Returned trial product(s) (used, partly used or unused including empty packaging material) must be stored separately from the non-allocated trial product(s) until drug accountability has been reconciled. The investigators will keep track of all received, used, partly used and unused trial products.

8.6 Destruction

Used and unused study drug may be destroyed at the site according to accepted pharmacy practice, local and national guidelines, using the site's destruction procedure.

8.7 Randomization, Stratification and Blinding

Patients will be consented and enrolled at the first study visit. Eligible patients will be randomized in a 1:1 allocation ratio to one of two treatment groups. Since this is a single center pilot study, randomization will not involve a permuted block design or any stratification.

Blinding of the study, with respect to treatment groups, will be preserved by the use of matching placebo. The investigator may be asked at the end of the trial if they had obtained any

information which may have led to the unblinding of treatment.

8.8 Unblinding

The investigator will be given access to the treatment code for their participants for emergency unblinding only. Any suspected study drug-related events should be treated as though the subject received sacubitril/valsartan. Randomization data are kept strictly confidential, accessible only to authorized persons, until the time of unblinding. Randomization codes will be provided to Novartis Pharmaceuticals at the time of study initiation. Upon completion of the double blind period, Novartis Pharmaceuticals will unblind data in the Argus safety database once database lock is completed and confirmed by Duke University Medical Center. This time frame is in accordance with Novartis standard operating procedures and unblinding will take place in coordination with the Duke study.

8.9 Concomitant Medication

Participants should be treated per standard care with their regular clinicians. However, the following medications should not be taken during the treatment period of this study: ACEI, ARB, aliskiren, or sacubitril/valsartan (other than blinded study drug), bile acid sequestering agents (e.g., cholestyramine), and nesiritide or intravenous nitrates (interrupt or discontinue study drug, as concomitant administration of sacubitril/valsartan with nesiritide or intravenous nitrates has not been studied).

The following medications should be used with caution during the study period: agents that raise potassium (e.g., potassium sparing diuretics, potassium supplements, mineralocorticoid receptor antagonists), and phosphodiesterase-5 inhibitors (may increase risk of hypotension).

9 RECRUITMENT AND SCREENING PROCEDURES

9.1 Common Recruitment Procedures

Individual meeting eligibility criteria will be approached regarding participation in this study.

9.2 Estimated Enrollment Period

This study will randomize approximately 50 subjects in the Duke University Health System in the U.S. The anticipated enrollment period is approximately 12 months.

9.3 Informed Consent

Study personnel will explain to eligible individuals the purpose of the study, study interventions and evaluations, and the potential risks and benefits of participation, and will answer any questions. If a subject agrees to participate in the study, they will review and sign the Duke University institutional review board (IRB) approved informed consent form (ICF).

9.4 Confidentiality and HIPAA Requirements

All information collected on study subjects will be stored in a confidential manner using the procedures in place at Duke University Hospital. Only approved study personnel will have access to data collected as part of the study. Consented study subjects will be identified by a subject ID number on all study documents.

9.5 Protections of Human Subjects

Protections for human subjects of research are required under Department of Health and Human Services (HHS) regulations at 21 CFR parts 50, 56, and 312.

9.6 Summary of the Risks and Benefits

Blood draws: The risks of drawing blood include bleeding at the puncture site, bruising and pain. These occur in a very small portion of the population.

Cardiac Magnetic Resonance Imaging (sub-study patients only): Serious reactions to the contrast agent used during some MRI tests are very rare. However, side effects are possible and include headache, nausea, dizziness, changes in taste, and allergic reactions. Rarely, the contrast agent can harm people who have severe kidney or liver disease. The substance may cause nephrogenic systemic fibrosis.

Sacubitri/valsartan: Sacubitri/valsartan is indicated to reduce the risk of cardiovascular death and hospitalization for heart failure in adult patients with chronic heart failure.^{7, 8, 16} Moreover, sacubitri/valsartan has been shown to reduce mortality in patients with heart failure and reduced ejection fraction (HFrEF).⁷ This agent is recommended in all patients with HFrEF (Class I, Level of Evidence B-R), unless contraindicated.¹⁷

Sacubitri/valsartan is teratogenic and contraindicated in pregnancy. Use of drugs that act on the renin-angiotensin system (of which sacubitri/valsartan is included) during the second and third trimesters of pregnancy reduces fetal renal function and increases fetal and neonatal morbidity and death. When pregnancy is detected, discontinue study drug as soon as possible. These adverse outcomes are usually associated with use of these drugs in the second and third trimesters of pregnancy. There is no information regarding the presence of sacubitri/valsartan in human milk, the effects on the breastfed infant, or the effects on milk production. Sexually active subjects must agree to use appropriate contraception as long as they are taking study drug. Medically acceptable contraceptives include:

- surgical sterilization (such as a tubal ligation or hysterectomy)
- approved hormonal contraceptives (such as birth control pills, patches, implants or injections)
- barrier methods (such as a condom or diaphragm) used with a spermicide, or
- Intrauterine device (IUD)

Sacubitril/valsartan should be used with caution in the setting of concomitant non-steroidal anti-inflammatory drugs, lithium, other potassium-sparing diuretics. Sacubitril/valsartan is contraindicated with use an ACEI, ARB, and should not be used with aliskiren in patients with diabetes.

In the PARADIGM-HF trial of patients with chronic heart failure with reduced ejection fraction, sacubitril/valsartan reduced the risk of cardiovascular mortality or heart failure hospitalization by 20%, as compared with guideline-indicated ACEI therapy (i.e., enalapril). In the PARADIGM-HF trial, use of sacubitril/valsartan was associated with a greater incidence of angioedema than the comparator drug enalapril (0.5% vs. 0.2%).⁷ The risk of angioedema with sacubitril/valsartan compared with enalapril was relatively greater among Black patients (2.4% vs. 0.5%). Patients with a history of angioedema are contraindicated from taking this drug. Trial data indicate adverse reactions occurring $\geq 5\%$ are hypotension, hyperkalemia, cough, dizziness, and renal failure. Symptomatic hypotension in PARADIGM-HF was more common among patients taking sacubitril/valsartan than enalapril (18% vs. 12%).⁷ In the PARAGON-HF trial, which tested the efficacy and safety of sacubitril/valsartan versus valsartan among patients with heart failure with preserved ejection fraction, no new adverse reactions were identified.⁸

10 VISIT SCHEDULE AND ASSESSMENTS

10.1 Baseline Evaluation, Enrollment and Randomization Visit

A schedule of assessments throughout the study is also provided in Appendix A.

Study Visit 1 (Enrollment and Randomization)

This visit will include the screening and informed consent process followed by a baseline assessment including:

- Demographics and medical history
- Review of medications patient is actively taking, and the doses
- Vital signs, including systolic and diastolic blood pressure, heart rate, height, weight
- EQ-5D quality of life questionnaire
- Residual COVID-19 symptoms
- Local laboratory testing, including the following:
 - Basic metabolic/renal function panel, including sodium, potassium, chloride, CO₂/bicarbonate, blood Urea Nitrogen (BUN), creatinine
 - High-sensitivity troponin

- Central laboratory testing, including the following
 - High-sensitivity troponin T
 - sST2
 - hs-CRP
 - PINP
 - Galectin-3
 - NT-proBNP
 - GDF-15
 - IL-6
 - CITP
- CMR examination, with intravenous gadolinium contrast (CMR sub-study patients only)
- Urine pregnancy test on women of childbearing potential

Patients will be initiated on blinded study medication, as dictated by systolic blood pressure. If systolic blood pressure is 100-120 mmHg at randomization, participants will receive sacubitril/valsartan 24/26 mg twice daily or matching placebo. If systolic blood pressure >120 mmHg at randomization, participants will receive sacubitril/valsartan 49/51 mg twice daily or matching placebo.

10.2 Follow-up Evaluations

Study Visit 2 (Titration Visit)

Visit 2 should take place within 7-21 days after the randomization visit.

Assessments at this visit include:

- Review of medications patient is actively taking, and the doses
- Vital signs, including systolic and diastolic blood pressure, and heart rate
- Local laboratory testing, including the following:
 - Basic metabolic/renal function panel, including sodium, potassium, chloride, CO2/bicarbonate, BUN, creatinine
- Urine pregnancy test on women of childbearing potential
- Adverse event monitoring, including hospitalizations
- Study medication adherence

If systolic blood pressure >100 mmHg and no symptomatic hypotension or deemed medication-related adverse effects, dose of study medication will be increased to the next highest dose of sacubitril/valsartan or matching placebo (i.e., patients originally receiving sacubitril/valsartan 24/26 mg twice daily will be increased to sacubitril/valsartan 49/51 mg twice daily; patients originally receiving sacubitril/valsartan 49/51 mg twice daily will be increased to sacubitril/valsartan 97/103 mg twice daily). Patients not meeting criteria for dose uptitration will remain on their original dose of study therapy, as tolerated. For patients who are reporting

symptomatic hypotension or other possible medication related adverse effects from study drug, the investigator may use their discretion in decreasing the dose of study drug to the next lowest dosing level.

Study Visit 3 (Final Study Visit)

Participants will return for a final study visit between 77 and 91 days (11-13 weeks) for the 12-week visit.

Assessments at this visit include:

- Review of medications patient is actively taking, and the doses
- Vital signs, including systolic and diastolic blood pressure, heart rate, weight
- EQ-5D quality of life questionnaire
- Residual COVID-19 symptoms
- Local laboratory testing, including the following:
 - Basic metabolic/renal function panel, including sodium, potassium, chloride, CO₂/bicarbonate, BUN, creatinine
- Central laboratory testing, including the following
 - High-sensitivity troponin T
 - sST2
 - hs-CRP
 - PINP
 - Galectin-3
 - NT-proBNP
 - GDF-15
 - IL-6
 - CITP
- CMR examination, with intravenous gadolinium contrast (CMR sub-study patients only)
- Urine pregnancy test on women of childbearing potential
- Adverse event monitoring, including hospitalizations
- Study medication adherence

Study Drug Interruption:

If a subject should stop taking study medication for any reason before completing the 12 weeks of study drug dosing, an attempt should be made to restart the study drug at the last tolerated dose when the subject is stable, per physician discretion. If the treating physician decides to stop study medication and start the patient on an ACEI, then a 36 hour wash-out period is required after the last dose of study drug before starting the ACEI. All subjects will complete all study assessments through study visit 3, regardless of whether they continue to receive the study drug for the full 12 weeks.

Unscheduled Visits:

If the Investigator determines that a participant should be brought to the clinic to be evaluated

for a potential change in study drug dose between scheduled study visits, an “unscheduled visit” should be done. Study drug dose changes will be recorded in the eCRF.

Assessments at this visit include:

- Interim history
- Review of medications patient is actively taking, and the doses
- Vital signs, including systolic and diastolic blood pressure, and heart rate
- Local laboratory testing, including the following:
 - Basic metabolic/renal function panel, including sodium, potassium, chloride, CO₂/bicarbonate, BUN, creatinine
- Adverse event monitoring
- Study medication adherence

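### No pregnancy test is scheduled in the 56 to 84 days between Visit 2 and the end of dosing; one added urine test, preferably on days 35 to 42, would be a cheap improvement

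*Combined protocol and SAP*

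**What the plan says.** Sections 10.1 and 10.2 and Appendix A place the test ("Urine pregnancy test on women of childbearing potential") at Visits 1, 2 and 3 and nowhere else. On timing, section 10.2 says "Visit 2 should take place within 7-21 days after the randomization visit" and, for Visit 3, "Participants will return for a final study visit between 77 and 91 days (11-13 weeks) for the 12-week visit". Section 8.1 sets dosing at 12 weeks, give or take one, so Visit 3 coincides with the end of treatment. Section 8.2 adds: "Participants will receive a sufficient supply of study drug at each study visit to last until the next study visit". The Visit 2 supply therefore covers the whole stretch to Visit 3, and no contact is scheduled within it.

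Section 9.6 says that sacubitril/valsartan "is teratogenic and contraindicated in pregnancy". It links the fetal harm mainly to use in the second and third trimesters, calls for prompt discontinuation once a pregnancy is found, and requires contraception in sexually active participants. Section 7.3 (items 7 and 8) excludes pregnant or breast-feeding women and women of childbearing age who will not use birth control. Section 12.12 stops drug on a confirmed pregnancy and follows it to its outcome.

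On interruptions, section 10.2 says "If a subject should stop taking study medication for any reason before completing the 12 weeks of study drug dosing", then "an attempt should be made to restart the study drug at the last tolerated dose when the subject is stable, per physician discretion". Unscheduled visits are for evaluating a participant "for a potential change in study drug dose between scheduled study visits". Neither the interruption paragraph nor the unscheduled-visit list names a pregnancy test, and neither forbids one.

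**The concern.** The stop-drug rules in sections 9.6 and 12.12 work only once a pregnancy is known. If a urine test turns positive about 14 days after conception, a Visit 2 test on days 7 to 13 cannot detect any conception on or after day 0, and a test on day 21 reaches only conceptions up to day 7. The Visit 3 test comes when drug is stopping anyway. For a conception that the woman does not notice, the scheduled tests can therefore do little to shorten exposure.

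What is at stake is fetal safety: possible exposure on drug in the part of pregnancy that section 9.6 itself links to the main harm. The efficacy analysis is not affected.

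**Working it through.** **Inputs from the protocol.** Visit 2 on day 7 to 21 and Visit 3 on day 77 to 91 (section 10.2); dosing for 12 weeks ± 1 week (section 8.1).

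**Assumptions not in the documents.** A urine test turns positive 14 days after conception (range 10 to 21). The second trimester starts at 13w0d (91 days) or 14w0d (98 days) of gestation, counted from 14 days before conception.

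**1. The plan's own window.** 11 × 7 = 77 and 13 × 7 = 91, so the weeks and days in section 10.2 agree with each other and with 12 ± 1 weeks of dosing.

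**2. Interval without a scheduled test.** Shortest 77 − 21 = 56 days; central 84 − 14 = 70; longest 91 − 7 = 84. Appendix A labels Visit 2 as week 1-2. Read as days 7 to 14, that gives 77 − 14 = 63 to 84 days.

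**3. Oldest pregnancy that Visit 2 can miss.** One rule is used throughout: a test on day T detects conceptions up to and including day T − lag. The earliest conception missed at Visit 2 is then on day (Visit 2 − lag + 1). Its gestation at Visit 3 is Visit 3 − (Visit 2 − lag + 1) + 14 = gap + lag + 13 days.

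| Visits 2/3 (days) | Gap | Lag 10 | Lag 14 | Lag 21 |
|---|---|---|---|---|
| 21/77 | 56 | 79 d = 11w2d | 83 d = 11w6d | 90 d = 12w6d |
| 14/84 | 70 | 93 d = 13w2d | 97 d = 13w6d | 104 d = 14w6d |
| 7/91 | 84 | 107 d = 15w2d | 111 d = 15w6d | 118 d = 16w6d |

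Days on drug past the 13-week / 14-week boundary:

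| Visits 2/3 (days) | Lag 10 | Lag 14 | Lag 21 |
|---|---|---|---|
| 21/77 | 0 / 0 | 0 / 0 | 0 / 0 |
| 14/84 | 2 / 0 | 6 / 0 | 13 / 6 |
| 7/91 | 16 / 9 | 20 / 13 | 27 / 20 |

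At a 14-day lag the exposure needs a gap above 91 − 27 = 64 days (13-week boundary) or 98 − 27 = 71 days (14-week boundary). The 15w6d case is a conception on day −6, before randomization. For a conception on day 0 and Visit 3 on day 91, gestation is 91 + 14 = 105 d = 15w0d, which is 14 or 7 days past the boundaries.

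**4. With one added test on day T.** Taking Visit 3 at its latest (day 91), the oldest pregnancy still missed has gestation 91 − T + lag + 13.

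| T | Lag 10 | Lag 14 | Lag 21 |
|---|---|---|---|
| 28 | 86 d = 12w2d | 90 d = 12w6d | 97 d = 13w6d |
| 35 | 79 d = 11w2d | 83 d = 11w6d | 90 d = 12w6d |
| 42 | 72 d = 10w2d | 76 d = 10w6d | 83 d = 11w6d |

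For lags of 10 to 14 days, any test day from 28 to 42 leaves no second-trimester exposure. For a 21-day lag a day-28 test leaves 97 − 91 = 6 days (13-week boundary only), and a test on day 35 or later leaves none.

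**5. Gestation when caught.** For a pregnancy just missed on day 7 and found on day 42: 35 + lag + 13 = 62 d = 8w6d at a 14-day lag and 69 d = 9w6d at 21 days. Both are in the first trimester.

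**6. Gaps with a test on days 35 to 42.** Visit 2 to the new test: 35 − 21 = 14 to 42 − 7 = 35 days. New test to Visit 3: 77 − 42 = 35 to 91 − 35 = 56 days. The longest gap falls from 84 to 56 days.

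**The case against.** The plan already has several layers of protection for a 12-week trial: exclusion, required contraception, three scheduled tests, mandatory discontinuation and follow-up to outcome. Nothing in the documents prescribes a mid-course test, so asking for one can be called a preference. The harm also needs a chain of events: contraceptive failure, assignment to active drug (about 25 of about 50), an early Visit 2 or late Visit 3, and a pregnancy unnoticed for many weeks. Section 7.2 asks for detectable troponin plus a factor such as age 60 or over, so women of childbearing potential may be few, although age is only one of six alternatives. Purely as an assumption, take 2 to 10 such women on active drug, 1 to 13% annual contraceptive failure and a relevant conception window of 7 to 21 days. The expected number of conceptions is then 2 × 0.01 × 7/365 ≈ 0.0004 to 10 × 0.13 × 21/365 ≈ 0.075, before requiring that the pregnancy go unnoticed. The consent text, which may tell women to report a missed period, is not available here.

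All of this stands, and it limits the point to an inexpensive improvement. It does not remove the gap: the trial already tests despite requiring contraception, and the question is where the tests fall.

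A reader might infer more than the documents support:

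- *That a requirement is breached.* The documents set no testing interval.
- *That any conception up to about day 14 reaches the second trimester on drug.* Conception on day 14 reaches 91 − 14 + 14 = 91 d = 13w0d only if Visit 3 is on day 91 and the 13-week boundary is used, and then with 0 days beyond it.
- *That section 12.12 is idle for a pregnancy first found at Visit 3.* Follow-up to outcome and recording of maternal and fetal events still apply; what is lost is the chance to shorten exposure.
- *That section 10.2 would put a woman known to be pregnant back on drug.* Section 12.12 requires discontinuation, and restart is discretionary. The gap concerns a pregnancy nobody has looked for.

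**Conclusion.** The point holds as a low-cost safety improvement. The 56 to 84 day interval follows directly from the protocol. The consequence rests on the assumed test lag and trimester boundary. At a 14-day lag, possible second-trimester exposure from a pregnancy missed at Visit 2 is nil on the shortest schedule, at most 6 days at central timing (13-week boundary only), and 13 to 20 days on the longest. Lags of 10 and 21 days move the longest case to 9 to 16 and 20 to 27 days. The event is unlikely, the number of women concerned is not stated, and no trial result depends on it. It merits action because the possible harm is serious and the remedy repeats a test the trial already uses.

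**What to change.** In section 10.2 and Appendix A, add one urine pregnancy test for women of childbearing potential between Visits 2 and 3, preferably on days 35 to 42. A home kit with a telephone report is enough. Hold study drug on a positive result until pregnancy is confirmed or ruled out.

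In the interruption paragraph of section 10.2, require a negative urine test in these women before interrupted drug is restarted, and add the test to the unscheduled-visit list.

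The cost is one kit and one brief call per woman of childbearing potential, one further test at any unscheduled visit or restart, and a short amendment. Days 28 to 34 would also work for lags of 10 to 14 days, but days 35 to 42 cover a 21-day lag as well. Endpoints, power and blinding are unaffected.

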11 OUTCOME DETERMINATIONS

11.1 Primary Endpoints

1. Relative change from baseline in high-sensitivity troponin T levels from randomization to 12 weeks.
2. Relative change from baseline in sST2 from randomization to 12 weeks.

11.2 Exploratory Endpoints

1. Change from baseline in high-sensitivity C-reactive peptide
2. Change from baseline in PINP
3. Change from baseline in Galectin-3
4. Change from baseline in NT-proBNP
5. Change from baseline in GDF-15
6. Change from baseline in IL-6
7. Change from baseline in CITP
8. Change from baseline in CMR measures (LVEF, LVEDVi, LVESVi, Native T1, Native T2)
9. Change from baseline in focal fibrosis by delayed-enhancement
10. Change from baseline in focal fibrosis as percentage of LV myocardial mass
11. Change from baseline in health related quality of life, as measured by EQ-5D utility score and EQ-5D visual analog scale

